11.5 Handling of missing data and drop-outs

There will be no imputation of missing data. We will not use false data. There will not be unused data. We will strive to publish all data.

12. QUALITY ASSURANCE AND CONTROL

The Sponsor is responsible for implementing and maintaining quality assurance and quality control systems with written SOPs and Working Instructions. The Sponsor is responsible for proper training of all involved study personnel.

12.1 Data handling and record keeping / archiving

12.1.1 Case Report Forms

Study data is recorded in Case Report Forms on paper (pCRF). Data entry will be done by the investigators who are responsible for the correctness of the data. If a person is enrolled to participate in the study, the personal record will be encoded, and the person given a randomization number. For each enrolled study participant a pCRF is maintained. All patient information and test results are recorded in the CRF. Only the participant number and the year of birth will be entered in the pCRF. The encryption process used for the pCRF are in accordance with Swiss guidelines for encryption. Hence, only the investigators and authorized persons have access to data.

The pCRFs are kept current to reflect subject status at each phase during the course of study. The investigators at the site are responsible for pCRF entries and have to sign their entries with initials and date of the entry according the specifications of the pCRF.

The informed consent will be obtained in wet ink during the screening visit and then uploaded to the clinical information system (KISIM) and filed into the TMF for recordkeeping.

Data transfer in excel tables for statistical evaluation is checked by double data entry. A printout of the excel sheet is added to the study documents and every data change in the electronic data should be assigned a new printout.

The randomization list will be stored electronically as a series of files labelled with the participant number that contains information on the randomization, with password-protected, logged access and an audit trail that will be stored electronically for 15 years. As this is an open-label trial, any physician can access the randomization list, and request details of the allocation of an individual patient.

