DSUR	Development safety update report
FNA	Fine needle aspiration
GCP	Good clinical practice
IB	Investigator's Brochure
Ho	Null hypothesis
HRA	Federal Act on Research involving Human Beings (in German: HFG, in French: LRH, in Italian: LRUM)
IEC	Independent Ethics Committee
IMP	Investigational Medicinal Product
IIT	Investigator-initiated Trial
ILIT	Intralymphatic immunotherapy
ITT	Intention to treat
PI	Principal Investigator
SCIT	Subcutaneous Immunotherapy
SDV	Source Data Verification
SmPc	Summary of Product Characteristics
SOP	Standard Operating Procedure
SPC	Summary of product characteristics
SUSAR	Suspected Unexpected Serious Adverse Reaction
TMF	Trial Master File
USZ	University Hospital Zurich

STUDY SCHEDULE

Table 1. Illustrating the study schedule with all interventions divided into the five visits. Patients will receive 6 SCIT injections as standard of care (not part of the study). 4-6 weeks later, the patients will be included in the clinical trials for assessment of immunological characteristics after a single ILIT or SCIT with subsequent fine needle aspiration (FNA), adverse event (AE) monitoring, and venous blood collection.

Visit / time point	1 Screening < 6 weeks of last SCIT	2 AIT	3 FNA	4 Follow-up	5 Follow up
		Day 0	Day 0-1	Day 7	Day 28
Required personnel	Nurse/MD	MD	MD	Nurse/MD	Nurse/MD
Informed consent	x				
Randomization	x				
Medical history	x				
Physical exam	x				
Incl./excl. criteria	x				
Blood samples		x	x	x	x
Pregnancy test		x			
AEs/Concomitant medication		x			x
Peakflow measurement		x*			
Injection: Study drug administration		x			
FNA (2x)			x**		
AE monitoring (1h observation at allergy unit after injection)		x			
Dispensing rescue medication		x			

* Peakflow measurement will be performed immediately before injection and 40 minutes after injection

** The FNA is performed 2, 6 or 24 hours after the Polvac™ ILIT or SCIT, and the injected (ILIT) or draining (SCIT) lymph node is used for FNA. For baseline reference, a contralateral lymph node is also aspirated.

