3.5 Rationale for the dosage, route, regimen

We will include grass pollen allergy patients with pre-seasonal short-term and pre-seasonal injection scheme with Polvac™ SCIT at the USZ Allergy Unit (Head: [name]). After the patients have received the full cycle of SCIT (six injections) as a part of standard care, they will be randomized into one of the two study groups for one additional injection, which is to be given 4-6 weeks after the last SCIT cycle injection. Depending on the group allocation, patients will receive allergen by SCIT (or by ILIT). *Figure 2* illustrates schematically the study design and *Figure 3* shows the flow chart for the study participants.

Polvac™ Doses:

- SCIT (n=15): 0.5 ml Polvac™ (max maintenance dose, 2000 U).
- ILIT (n=15): 0.1 ml Polvac™ (400 U).

The SCIT dose is chosen as this is the recommended and standardized treatment dose for patients receiving SCIT with Polvac™ for treatment of grass pollen allergy. The ILIT dose is 1/5th of the maintenance SCIT dose. This has been safely administered in four patients treated off-label with Polvac™ at the USZ allergy in 2023 ([name] and [name], personal communication). These four patients received three injections in a dose escalating manner and with four-week intervals. The doses were 1/15th, 1/10th and finally 1/5th of the maintenance SCIT dose. An ILIT dose of 1/15th of the maintenance SCIT dose was safely administered three times in 30 patients in the aforementioned ongoing study with Polvac™ ILIT (BASEC 2021-02301).

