6. STUDY DESIGN

6.1 General study design and justification of design

This is a prospective, comparative, clinical open label pilot study. From patients with grass pollen allergy who undergo a pre-seasonal SCIT scheme with Polvac™ Grass+RyeSCIT at the USZ Allergy Unit, 30 patients will be recruited for the study that is illustrated in Figure 2.

Four to six weeks after end of SCIT treatment (at maximal maintenance dose), the patients will be randomized to one out of two treatment groups and receive one additional allergen injection. Fifteen patients will be allocated to receive another subcutaneous injection with 0.5 ml (2000 U) Polvac™

Grass+Rye. The other 15 patients will be allocated to receive an intralymphatic injection of 0.1 ml Polvac™ Grass+Rye with 400 U allergen. Both SCIT and ILIT injections are performed by ultrasound-guidance as to assure injection into the lymph node (ILIT) or 1 cm next to the lymph node (SCIT).

The FNA of lymph node tissue will be conducted at 2, 6 or 24 hours after allergen injection. At the same time, FNA of a contralateral lymph nodes will be performed as baseline. Venous blood will be sampled at all visits: at baseline as well as after 2, 6 or 24 hours, after 7 days and after 28 days of the allergen ILIT or SCIT. The FNA is performed by ultrasound-guidance.

[figure not shown]

Figure 2. Study design illustrated schematically the open-label clinical pilot study for assessment of immunological and inflammatory responses to a single ILIT or SCIT in patients receiving grass pollen immunotherapy with Polvac™ Grass+Rye.

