6.2 Methods of minimising bias

6.2.1 Randomisation

All patients who give consent for participation and who fulfil the inclusion criteria will be randomized to either SCIT or ILIT treatment group with a 1:1 allocation. The randomisation list will be computer-generated by a statistician using a permuted block design (groups of six). Before trial initiation, randomisation envelopes will be given to the study physician who will then be responsible of envelope storage and appropriate use. Allocation concealment will be ensured as the randomisation envelopes will not be opened before the patient has been recruited into the trial, which takes place after screening has been completed.

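### Section 12.1.1 opens the randomisation list to any physician and Table 1 randomises before eligibility is settled, so the concealment claimed in 6.2.1 is not secured

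*Combined protocol and SAP*

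**What the plan says.** On concealment, section 6.2.1 states: "Allocation concealment will be ensured as the randomisation envelopes will not be opened before the patient has been recruited into the trial". It adds that recruitment follows completed screening. On the envelopes: "randomisation envelopes will be given to the study physician who will then be responsible of envelope storage and appropriate use".

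On the list, section 12.1.1 describes electronic files, one per participant number, with a password, logged access and an audit trail. It continues: "As this is an open-label trial, any physician can access the randomization list, and request details of the allocation of an individual patient".

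On timing, Table 1 has the rows "Randomization x" and "Incl./excl. criteria x", both marked in the Visit 1 (screening) column and in no other. Section 3.5 says that after the full SCIT cycle "they will be randomized into one of the two study groups for one additional injection". Section 6.1 says: "Four to six weeks after end of SCIT treatment (at maximal maintenance dose), the patients will be randomized". Section 8.1 also places randomisation after the cycle, at four weeks. The visit-by-visit lists in 9.3 name randomisation at no visit.

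On eligibility, 7.1 ties some criteria to the injection rather than to screening: infection present at the treatment visit, and an allergic reaction in the preceding 4 days. The pregnancy test is a Visit 2 procedure (Table 1, 9.3.2). Section 7.4 leaves exclusion after a change in eligibility to the physician's discretion and allows replacement.

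**The concern.** Blinding and concealment are different protections. An open-label trial cannot hide the arm once it has been given, but it can and should hide the arm that comes next. Section 12.1.1 gives the lack of blinding as the reason for opening the list. Read as written, that covers allocations not yet made. Closed envelopes protect nothing if the same sequence can be read elsewhere.

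The timing question is separate. If the arm is assigned at Visit 1 while some criteria can be judged only at Visit 2, the decision to keep or drop a patient is made with the arm known.

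Comparing ILIT with SCIT is the primary objective (4.2), and 11.4 plans comparative tests between the arms. Foreseeable allocation, or discretionary exclusion with the arm known, would let two groups of 15 differ for reasons other than chance. Section 11 defines no analysis set that would keep excluded patients in view.

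**Working it through.** The plan gives no figure to reproduce here. The check sets the sections side by side and makes one count.

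**List access**
- 6.2.1: concealment rests on the envelopes alone.
- 12.1.1: physicians may access the list. The second half of the sentence, on asking about an individual patient, fits look-up after allocation. The first half grants the list itself and sets no such limit.
- The password does not exclude physicians, who are granted access. Logging and the audit trail show afterwards who looked; they do not prevent it. Nothing says that a participant's file becomes readable only after that participant has been randomised.

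**Order of events if Table 1 is followed**
- Randomisation and the general eligibility check: Visit 1.
- Injection: Visit 2, at least 1 day later (9.3.2).
- Infection at the treatment visit: always settled after randomisation, because Visit 2 is never on the same day as Visit 1.
- Pregnancy test: also after randomisation. The result is objective, so the issue is loss after randomisation, not steering.
- Allergic reaction in the last 4 days: let Visit 1 fall d days before injection. The window lies wholly after Visit 1 when d ≥ 5, and partly after it when d is 1 to 4.
  - Section 9.3.1 permits d = 1 to 29. Days with the whole window after Visit 1: 29 − 4 = 25 of 29.
  - If Visit 1 must also fall within the four-to-six-week interval of 6.1, and the injection too (3.5), the gap is at most 42 − 28 = 14 days: 14 − 4 = 10 of 14.
  - Section 8.4 lets screening be combined with a planned SCIT injection. The gap is then at least 28 days, and the whole window comes after screening.

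These are counts of permitted days, not estimates of how often each will be used.

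**Order of events under 3.5, 6.1 and 8.1**

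Randomisation comes after the SCIT cycle, but no visit is named, and 9.3 does not supply one. The site therefore has no single instruction on when to open the envelope.

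**The case against.** The strongest reply is that 12.1.1 describes ordinary look-up in an unblinded trial. Files are kept per participant, a number is given on enrolment, and the sentence ends with an individual patient's allocation. That may well be the intention. What stands is that intent is uncertain; what does not is that the text as written already protects future allocations.

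On timing, the reply is that one table mark is set against three sections and that 6.2.1 puts recruitment after screening. This is fair. A reader might infer that Table 1 contradicts 6.2.1, but the mark can be read as the end of the screening visit. The gap is that eligibility stays open beyond that visit.

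Four stronger readings are not supported:
- **Block size.** A reader might count the fixed block of six as part of the defect. Predictability within a block is a property of blocking in any open-label trial. It depends neither on who can read the list nor on the visit, and the changes proposed here leave it as it is.
- **A 60-day gap.** Section 7.2 allows screening up to 60 days ahead, and a reader might count over that range. Injection is due within six weeks (42 days) of the last SCIT injection, and Table 1 heads Visit 1 as under six weeks from it. Randomisation on days 43 to 60 before injection would precede the end of the cycle, contrary to 3.5, 6.1 and 8.1.
- **Envelope holder.** A reader might infer that the recruiting physician holds the envelopes. Section 6.2.1 names the study physician, 14.2.1 gives recruitment to the Allergy Unit team, and nothing says that these are the same person.
- **Replacements.** A reader might say that no rule exists. Section 6.2.1 randomises every eligible consenting patient from the list, which covers a replacement by implication. Only an explicit statement is missing. Section 8.5 already records the timing and reason of withdrawals, so reporting by arm is the only addition.

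**Conclusion.** The point holds as two defects of wording and schedule that, if followed literally, would defeat the concealment that the protocol claims. It should be corrected before enrolment. It does not show that allocation will be subverted.

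The size of any bias cannot be derived from the documents. The consequence is limited: this is a descriptive pilot with no single primary endpoint (4.2, 11.1), the primary readouts are laboratory measurements on stored samples, and the contralateral node and the pre-injection blood sample absorb part of any difference between the groups. Steering could act only through clinical traits visible to the physician. The safety reactions in 5.4, rated by clinicians and patients, do not have the same laboratory buffer.

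The first part rests on reading 12.1.1 as written. The second is conditional on Table 1 being the operative schedule. Figures 2 and 4 were not available for this check; a randomisation step shown there would need reconciling too.

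**What to change.** 1. In 12.1.1, restrict the full list to the statistician or another person not involved in enrolment. Let physicians see an allocation only after that patient has been randomised.
2. Reconcile Table 1 with 3.5, 6.1, 6.2.1, 8.1 and 9.3 so that the envelope is opened at Visit 2, after the existing eligibility criteria are re-checked and before the syringe is prepared.
3. State that a replacement takes the next allocation in sequence, and report post-randomisation exclusions by arm and reason.

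A different envelope holder is optional.

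**Cost.** Most of this is wording, plus a list that runs past 30.
- Visit 2 may run somewhat longer. Of its 120 minutes, at least 30 separate preparation from use (8.1.3) and 60 are observation, leaving 120 − 30 − 60 = 30 for steps that cannot be done during the preparation interval.
- For treatment before 09:00 the drug may be supplied the day before (8.1.1). Both arms use the same undiluted vial (Table 2), so supply does not need the arm, but the envelope must be accessible that morning.
- The split may depart slightly from 15:15. If one of 30 allocated patients is replaced from a new block of six, the replacement falls in the same arm with probability 3/6 = 0.5, giving 15:15 or 14:16 equally often.

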12.1.2 Specification of source documents

All data will be registered in a series of pCRFs including patient questionnaires and laboratory analysis that will be considered as source data. The source documents include the electronic medical records on site, as well as the study-specific documents and data collected during the visits, which are recorded directly via questionnaires or by the study-specific tests. The relevant source documents from the electronic medical records are printed out, signed by the investigator and collected in a separate folder. This folder is stored in a lockable cabinet to which only the study team has access.

Data from the pCRF are filed in to the TMF for recordkeeping and additionally in the clinical information system (KISIM).

12.1.3 Record keeping / archiving

All study documents (essential documents and site documents) are archived in the Department of Dermatology of the University Hospital Zurich for a minimum of 10 years after study termination or premature termination of the clinical trial.

12.2 Data management

The project site will retain all essential documents according to national legal and regulatory requirements, including source data and CRF. Source data are all information in original records and certified copies of original records of clinical findings, observations, or other activities necessary for the reconstruction and evaluation of this project. All essential documents are stored until 10 years after the termination of the project, during which time the project leader guarantees access and availability of the data at any time.

12.3 Monitoring

The trial monitoring in Zurich is done by the Clinical Trials Center, USZ.

12.4 Audits and Inspections

The investigators and sponsor allow direct access to source documents for monitoring, audit and inspection by GCP units, health authorities, ethics committees, data authorities and other medical autothrities. All involved parties must keep the participant data strictly confidential.

12.5 Confidentiality, Data Protection

Health-related personal data captured during this project from participants are strictly confidential and disclosure to third parties is prohibited. Coding will safeguard participants' confidentiality.

The electronic case report forms (CRFs) will be entered into an excel-based database. Confidentiality will be ensured by entering only coded data into the analysis set. The coded data will be password-protected and accessible to the sponsor, the medical investigators and the project researchers. The statistician will obtain copies of the Excel database after the data entry has been completed. Coded research data are not considered part of the essential documents and will be stored on a central data server at the USZ with restricted access: \\fs-group\der_forschungen\DER_FL_Immunotherapie

The code for data generated at USZ is kept with the sponsor.

12.6 Storage of biological material and related health data

Data from this trial will be stored for 10 years in electronic form after completion of the trial. The collected blood and FNA samples are to be used and analysed exclusively in the current study. No material or data transfer to other or future projects are foreseen. The collected blood samples and FNA in this study

is not identified by participant name but by a unique participant number and is appropriately stored in a restricted area only accessible to the authorized personnel.

13. PUBLICATION AND DISSEMINATION POLICY

A clinical study report will be prepared covering clinical aspects and summarizing all findings of the clinical study. The content has to be treated as strictly confidential. The information gathered in this study is considered confidential and is the property of the sponsor. Within 12 months of completion of the trial, trial results will be entered into the international clinical trials registry (SNCTP and clinicaltrials.gov).

We aim to publish the results of this study in a peer reviewed journal, irrespective of the outcome.

There is a publication delay of up to 3 months while partners or interested parties may evaluate the commercial potential of results from this clinical trial. Authorship will follow Vancouver rules. Partners in the project will be authors on the publication; contributors will be mentioned under acknowledgements (there is a group of researchers that is credited without being authors. that is where they may be).

We confirm if gender effects are observed, they will be published in the final study report. If none are observed, this will be published as well.

14. FUNDING AND SUPPORT

14.1 Funding

The Department of Dermatology of the University Hospital of Zurich ([name] [name]) will support the study with CHF ca. CHF 30'000 if required through University funds. The sponsor will guarantee for ca. 50'000 through overhead from various project-unrelated contracted research with biotech.

The Truus und Gerrit van Riemsdijk Stifung, Vaduz will support the study with 20'000 CHF.

We submitted a project-grant application to EMDO Stiftung (CHF 50'000), and we are planning an application to Theodor und Ida Herzog Egli Stiftung for the same amount (submission deadline 30.4.2023).

14.2 Other Support

14.2.1 Cooperation with other institutes

All clinical and experimental infrastructures required to conduct the study are available in Department of Dermatology, USZ/UZH and at the associated lab at SIAF, Davos.

We will collaborate with [name]. med. [name] and his team the Allergy Unit USZ CIRCLE for screening, recruitment, treatment and monitoring of patients included in the study. Such a collaboration is already existing as part of already running randomized double-blind placebo controlled trial on the efficacy of grass pollen ILIT. Hence, all personnel and infrastructure required in the current project, is already established and available.

We will also collaborate closely with the UZH-Institute SIAF, Davos, for the analysis of blood and lymph node cells by mass cytometry (CyTOF). Since four years, SIAF as being building of expertise on CyTOF through [name] and [name]. med. [name].

Finally, we are and will consult [name] [name] from the Department of Respiratory Diseases and Allergy at the University of Aarhus, Denmark. [name] is worldwide perhaps recognized as the most experienced researcher on ILIT. We have discussed the trial design for the current study with [name].

15. INSURANCE

Insurance will be provided by the Sponsor /

Patients will be covered by an insurance (*Pauschalvertrag*) for clinical trials, issued by Zurich Versicherungs-Gesellschaft AG. The policy number is 14.970.888.

17. APPENDICES

001. Product description Polvac™

002. SmPC Polvac™

003. Product description of rescue medication

1. Product description "Allergie-Notfallset"
2. Product description "Fenistil Gel 1%"

004. Drug Accountability Log

005. CRF and questionnaire for participants

006. Patient questionnaires in German (days 0-3 post ILIT)
